10.2.6 Area of Safety Interest

Area of safety interest (ASI) will be summarized by categories. Detailed information about the search criteria is provided in [Appendix B](#).

The final list will be based on the most updated final version of RZB product Safety Statistical Analysis Plan, which is consistent with the most updated RZB Risk management plan.

10.3 Analysis of Laboratory Data

The clinical laboratory tests defined in the protocol operations manual (e.g., hematology, clinical chemistry, and urinalysis) will be summarized.

Each laboratory variable will be summarized for all time points (starting with Baseline) in Period A and B, with the number of non-missing observations, mean and standard deviation, median, minimum and maximum. Mean change from baseline to each applicable post-baseline visit will be summarized for selected laboratory variables, with the number of observations, baseline mean, and visit mean. The change from baseline mean, standard error, and 95% confidence interval will be presented for the mean change from baseline within each treatment group and difference between treatment groups.

Laboratory parameters will be tabulated using shift tables either by National Cancer Institute (NCI) Common Terminology Criteria (CTC) or categorized as low, normal, or high based on the normal ranges of the laboratory used for each sample. A shift table from baseline either to the worse value (based on NCI-CTC) during treatment or to minimum and maximum value (based on normal range), will be created in Period A and B. A similar shift table will be provided to summarize shifts from baseline to the final post-baseline value in Period A and B.

Laboratory abnormalities meeting NCI-CTC Grade 3 and 4 will be summarized in Period A (Safety Populations), B (Safety B Populations) and during the administration of risankizumab (ALL RZB Populations).

Laboratory abnormalities will be evaluated based on Potentially Clinically Significant (PCS) criteria ([Appendix C](#)), in Period A (Safety Populations), B (Safety B Populations) and during the administration of risankizumab (ALL RZB Populations). For each laboratory PCS criterion, the number and percentage of subjects who have a laboratory value meeting the criteria will be summarized. Listings will be provided to summarize subject-level laboratory data for subjects meeting PCS criteria.

In addition, the number and percentage of subjects meeting criteria for potential hepatotoxicity during the Treatment Period will be provided.

- ALT > 3 × ULN, > 5 × ULN, > 10 × ULN, > 20 × ULN
- AST > 3 × ULN, > 5 × ULN, > 10 × ULN, > 20 × ULN
- TBL > 1.5 × ULN, > 2 × ULN
- ALT and/or AST > 3 × ULN and TBL > 1.5 × ULN
- ALT and/or AST > 3 × ULN and TBL > 2 × ULN
- ALT > 3 × ULN and TBL > 1.5 × ULN
- ALT > 3 × ULN and TBL > 2 × ULN
- Alkaline phosphatase > 1.5 × ULN

A listing will include all subjects who met any of the following four criteria:

- ALT > 3 × ULN, or
- AST > 3 × ULN, or
- ALP > 1.5 × ULN, or
- Total bilirubin > 1.5 × ULN.

A listing of possible Hy's Law cases, defined as those who meet all of the following conditions will be provided.

- ALT of $> 3 \times \text{ULN}$ or AST of $> 3 \times \text{ULN}$,
- Total bilirubin $\geq 2 \times \text{ULN}$,

Urinalysis and pregnancy testing results will be provided in listings only.

10.4 Analysis of Vital Signs

Vital sign measurements of systolic and diastolic blood pressure will be summarized.

Each vital sign variable will be summarized for all time points (starting with Baseline) with the number of non-missing observations, mean and standard deviation, median, minimum and maximum, in Period A (Safety Populations) and B (Safety B Populations). Mean change from baseline to each applicable post-baseline visit will be summarized for each vital sign variable, with the number of observations, baseline mean, and visit mean. The change from baseline mean, standard error, and 95% confidence interval will be presented for the mean change from baseline within each treatment group and difference between RZB vs. placebo.

Vital sign variables will be evaluated based on Potentially Clinically Significant (PCS) criteria ([Appendix C](#)). For each vital sign PCS criterion, the number and percentage of subjects who have a vital sign value meeting the criteria will be summarized in Period A (Safety Populations), B (Safety B Populations) and during the administration of risankizumab (ALL RZB Populations). Listings will be provided to summarize subject-level vital sign data for subjects meeting PCS.

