7.5 Statistical Analyses for Safety

The safety analyses will be carried out using the Safety_G and Safety_S populations for Study-G and Study-S, respectively, and will be based on treatments the subjects actually received. Safety will be assessed by AEs, physical examination, laboratory assessments, and vital signs. Analysis details will be specified in the SAP.

TEAEs in each analysis period is defined as follows:

A TEAE in Period A for both Study-G and Study-S is defined as any AE with an onset date on or after the first dose of study drug in Period A and within the minimum of 140 days after the last dose of study drug in Period A and first dose of study drug in Period B.

A TEAE in Period B for both Study-G and Study-S is defined as any AE with an onset date on or after the first dose of study drug in Period B and within 140 days after the last dose of study drug in Period B.

A TEAE during the administration of risankizumab (i.e., among the ALL_RZB_G and ALL_RZB_S Population) is defined as any AE with an onset date on or after the first dose of risankizumab and within 140 days after the last dose of risankizumab.

The number and percentage of subjects experiencing TEAEs will be tabulated using the MedDRA SOC and preferred term, by severity, and by relationship to the study drug as assessed by the investigator. Summaries (including percentages and events per 100 patient-years) of SAEs, deaths, AEs leading to discontinuation and ASI will be provided as well. Pre-treatment SAEs will be summarized separately.

For laboratory tests and vital signs, mean change from baseline and percentage of subject with evaluations meeting predefined Potentially Clinically Significant criteria will be summarized. A listing of all subjects with any laboratory value that is above Grade 3 of CTCAE will be provided.

Additional details for the safety analysis will be provided in the SAP.

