3.9 Vital Signs

Vital sign determinations of systolic and diastolic blood pressure, pulse rate, respiratory rate, and body temperature will be obtained at visits as specified in Section 2.1. Blood pressure and pulse rate should be measured after the subject has been sitting for at least 3 minutes.

Measurements should be assessed consistently throughout the study. Vital signs measurements determined prior to dosing on Baseline/Day 1 or specify timing will serve as baseline.

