Appendix C. Potentially Clinically Significant Criteria for Safety Endpoints

The criteria for Potentially Clinically Significant (PCS) laboratory findings are described in Table C-1 and Table C-2, and the PCS criteria for vital sign findings are described in Table C-3.

Table C-1. Criteria for Potentially Clinically Significant Hematology Values

Hematology Variables	Units	Definition of Potentially Clinically Significant Current (Version 4.03) NCI CTCAE Grade 3 or Greater	
		Very Low	Very High
Hemoglobin	g/dL	< 8.0	
Platelets count	10 ⁹ /L	< 50.0	
WBC count	10 ⁹ /L	< 2.0	
Neutrophils	10 ⁹ /L	< 1.0	
Lymphocytes	10 ⁹ /L	< 0.5	

Note: A post baseline value must be more extreme than the baseline value to be considered a potentially clinically significant finding.

Table C-2. Criteria for Potentially Clinically Significant Chemistry Values

Chemistry Variables	Units	Definition of Potentially Clinically Significant Current (Version 4.03) NCI CTCAE Grade 3 or Greater	
		Very Low	Very High
TBL	mcmol/L		$> 3.0 \times \text{ULN}$
ALP	U/L		$> 5.0 \times \text{ULN}$
SGOT/AST	U/L		$> 5.0 \times \text{ULN}$
SGPT/ALT	U/L		$> 5.0 \times \text{ULN}$
Albumin	g/L	< 20	
Glucose	mmol/L	< 2.2	> 13.9
Triglycerides	mmol/L		> 5.7
Creatinine	mcmol/L		$> 3.0 \times \text{ULN} (> 3.0 \times \text{BL})$
Sodium	mmol/L	< 130	> 155
Potassium	mmol/L	< 3.0	> 6.0
Calcium	mmol/L	< 1.75	> 3.1
CPK	U/L		$> 5.0 \times \text{ULN}$
Total Cholesterol	mmol/L		> 10.34
GGT			$> 5.0 \times \text{ULN}$

Note: A post baseline value must be more extreme than the baseline value to be considered a potentially clinically significant finding.

Table C-3. Criteria for Potentially Clinically Significant Vital Sign Values

Vital Signs Variables	Criterion	Definition of Potentially Clinically Significant
Systolic Blood Pressure (mmHg)	Low	Value ≤ 90 mmHg and decrease ≥ 20 mmHg from Baseline
	High	Value ≥ 160 mmHg and increase ≥ 20 mmHg from Baseline
Diastolic Blood Pressure (mmHg)	Low	Value ≤ 50 mmHg and decrease ≥ 10 mmHg from Baseline
	High	Value ≥ 100 mmHg and increase ≥ 10 mmHg from Baseline

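### SAP 10.4 summarises two of the five vital signs collected, gives no reason, and does not list the narrowing among the changes from the protocol

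*SAP*

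**What the plan says.** Protocol 3.5 and SAP 3.4 both list vital signs as a safety evaluation, and neither limits them to blood pressure. What is measured is set out in Operations Manual 3.9: "Vital sign determinations of systolic and diastolic blood pressure, pulse rate, respiratory rate, and body temperature will be obtained at visits". The activity schedule (Protocol Appendix D) places vital signs at every site visit from Screening to Week 52.

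Protocol 7.5 commits to an analysis: "For laboratory tests and vital signs, mean change from baseline and percentage of subject with evaluations meeting predefined Potentially Clinically Significant criteria will be summarized". The same section leaves analysis details to the SAP.

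SAP 10.4 begins "Vital sign measurements of systolic and diastolic blood pressure will be summarized". It then specifies descriptive statistics by time point, and mean change from baseline with standard error and 95% confidence interval "within each treatment group and difference between RZB vs. placebo". Listings are limited to subjects who meet the potentially clinically significant (PCS) criteria. Appendix C, Table C-3, has PCS criteria for systolic and diastolic pressure only. SAP 10.5 states that there are no other safety analyses. SAP 14.1 lists two changes from the protocol, both about efficacy subgroups, and the version history in SAP 14.0 does not mention vital signs.

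**The concern.** Safety is part of the primary objective, and vital signs are one of its named components. If SAP 10.4 is programmed as written, three of the five recorded measurements go into the database and appear in no planned output. A reader of the study report who knows the protocol would expect a table of mean change for pulse, respiratory rate and temperature. That reader would find none, and no explanation.

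The timing gives the omission some weight. The randomised comparison with placebo exists only up to Week 16, after which every subject receives risankizumab. A placebo contrast on these measurements can come only from the Week 4 and Week 16 visits, and few other safety measurements are scheduled then.

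**Working it through.** No formula or stated figure is involved. The check is a comparison of texts.

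**Step 1. Collected against analysed.**

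| Vital sign | Collected (Operations Manual 3.9) | Named in SAP 10.4 | PCS criterion in Table C-3 |
|---|---|---|---|
| Systolic blood pressure | yes | yes | yes |
| Diastolic blood pressure | yes | yes | yes |
| Pulse rate | yes | no | no |
| Respiratory rate | yes | no | no |
| Body temperature | yes | no | no |
| Count | 5 | 2 | 2 |

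Collected but not named for analysis: 5 − 2 = 3.

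**Step 2. Does another planned output pick up the three?** The listings in SAP 10.4 depend on PCS criteria, and the three signs have none. SAP 10.5 excludes further safety analyses. By contrast, SAP 10.3 expressly assigns urinalysis and pregnancy results to listings. The one remaining route is adverse event reporting: under Protocol 6.1 a vital-sign change counts as an adverse event if it leads to discontinuation, needs medical intervention, meets protocol criteria or is judged an adverse event by the investigator. Such events reach the by-group treatment-emergent tables in SAP 10.2. The measured values do not.

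**Step 3. Could SAP 10.4 be read more widely?** Its second paragraph says "Each vital sign variable will be summarized for all time points (starting with Baseline"). Taken alone, that could mean all five. It follows directly on a sentence naming two variables, and Table C-3 contains the same two, so the narrow reading is the natural one. If the wider one is intended, the text does not make that clear.

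**Step 4. What else is scheduled at Weeks 4 and 16** (Protocol Appendix D, Operations Manual 2.1)?

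- Haematology and chemistry: Screening, Baseline, Week 28, Week 52/Premature Discontinuation.
- Urinalysis and ECG: Screening only.
- Physical examination: Screening, Baseline, Week 52/Premature Discontinuation.
- At Weeks 4 and 16 themselves: vital signs, adverse event assessment, urine pregnancy test where applicable, and post-dose observation for hypersensitivity.

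Operations Manual 6.5 puts dosing after the other visit procedures. Week 16 vital signs therefore precede the first open-label dose and still belong to the randomised comparison.

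**Step 5. Is the narrowing declared?** SAP 14.1 has two entries: added efficacy subgroups and a corrected baseline sPGA-G subgroup. Neither concerns vital signs.

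**The case against.** The strongest reply is that no commitment is broken. Protocol 7.5 does not enumerate the vital signs and hands the detail to the SAP, and the Operations Manual governs collection, not analysis. Choosing which variables to tabulate is then the delegated detail. SAP 10.3 likewise restricts mean change to selected laboratory variables. This stands to the extent that a reader who inferred a direct contradiction between protocol and SAP would go too far. It does not explain why three of five components have no output at all. In SAP 10.3, laboratory variables outside the selected set still receive descriptive summaries.

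A second reply is that accepting PCS criteria for blood pressure alone concedes that the SAP may select. That is partly right, but the protocol ties PCS percentages to predefined criteria, so signs without criteria drop out naturally. Mean change needs no criterion.

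Three stronger inferences are tempting, and the documents do not support them:

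- **The three signs are never compared with placebo in any form.** Changes that qualify as adverse events are compared by treatment group.
- **Most of the objective randomised safety data are discarded.** The data are still collected, and three of five is a count of components, not of information. Laboratory tests and a physical examination also occur at premature discontinuation visits, and unscheduled laboratory tests and symptom-directed examinations are allowed at any time.
- **Omitting temperature weakens detection of infection.** Protocol 2.2 says infection risk is monitored through adverse events, and SAP Appendix B has several infection categories as areas of safety interest. Week 4 readings come about four weeks after the preceding scheduled dose and Week 16 readings about twelve weeks after. Mean temperature at those visits would not show infections in between.

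Nor can the omitted comparisons be called informative in a quantified sense. The documents give no standard deviation for any vital sign and no threshold that would make a difference important.

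**Conclusion.** The point holds as an undeclared and unexplained narrowing of a named safety endpoint. Three of five collected vital signs have no planned summary, between-group difference or listing of measured values, including at the two post-baseline visits of the placebo-controlled period. The conclusion rests on the narrow reading of SAP 10.4, which its opening sentence and Table C-3 both favour, and on no further change being recorded elsewhere in SAP 14.

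Its weight is low. These are descriptive safety tables. Nothing in the primary or ranked secondary analyses, the type I error control or the sample size depends on them. It is an improvement worth making because it costs almost nothing, and not a defect that threatens the trial's conclusions.

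**What to change.** In the first sentence of SAP 10.4, add pulse rate, respiratory rate and body temperature to the two blood pressures. The descriptive and change-from-baseline tables specified in the rest of the section then cover all five signs, including the difference from placebo. Table C-3 may stay as it is.

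If the sponsor prefers to keep the summary to blood pressure, the alternative is to record the restriction and its reason in SAP 14.1. That removes the lack of declaration but leaves the three signs unreported, so the first option is better.

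The cost is one amended sentence and extra rows in tables already planned. No data collection, visit or clinical rule changes.

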2.2 Study Design Overview

This is a Phase 4, multicenter, randomized, double-blind, placebo-controlled study examining the effect of RZB in adult subjects with moderate to severe genital psoriasis (Study-G) or moderate to severe scalp psoriasis (Study-S).

[figure not shown]
Participants will receive 150 mg of RZB (for those randomized to risankizumab) or matching placebo (for those randomized to placebo) subcutaneously at Baseline and Week 4. Starting at Week 16, all subjects will receive 150 mg of RZB every 12 weeks until the last dose at Week 40.

The duration of the studies will be approximately 64 weeks. Each study comprises a 30-day Screening Period, a 16-week double-blind placebo-controlled treatment period (Period A), a 36-week open-label treatment period (Period B), and an 8-week Follow-up Period. The follow-up phone call (20 weeks following the last dose of study drug) during the trial will not be required for any subject who initiates commercial RZB or continues

under another AbbVie protocol for the purposes of continued treatment (i.e., CTE or CTPP OLE).

The schematic of the study is shown in [Figure 1](#).

Figure 1. Study Schematic

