If there is a stratum with zero subjects in either treatment group, the 0 count will be replaced by 0.1 in order to prevent dividing by 0 in the above equations, as suggested in Greenland & Robins. In case of any stratum with zero subjects in both treatment groups, the corresponding stratification factor will not be controlled.

For continuous variables, the Baseline mean, visit mean, as well as the Least Square (LS) mean, 95% confidence interval (CI) and Standard Error (SE) of the mean, will be reported for each ITT Population. The comparisons between RZB and placebo will be analyzed using Mixed-Effect Model Repeated Measurement (MMRM) method, adjusting for the fixed effects of treatment, actual values of stratification factors at Baseline, Baseline value, visit and treatment by visit interaction as covariates.

"Baseline" refers to the last non-missing observation on or before the date of the first administration of study drug, or the date of randomization if no study drug is administered.

For analyses by stratification factors used for randomization, any subject who is randomized within an incorrect stratum will be analyzed according to the actual stratum to which the subject belongs.

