10.5 Other Safety Analyses

There will be no other safety analyses for this study.

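### SAP 10.4 names no baseline covariate for the risankizumab-versus-placebo difference in blood pressure change; adjusting for baseline would give a modest precision gain at almost no cost

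*SAP*

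**What the plan says.** SAP 10.4 limits the vital-sign analysis to blood pressure: "Vital sign measurements of systolic and diastolic blood pressure will be summarized". After descriptive statistics by time point and mean changes by visit, it continues: "The change from baseline mean, standard error, and 95% confidence interval will be presented", and these are to be "presented for the mean change from baseline within each treatment group and difference between RZB vs. placebo". It mentions no model, least-squares mean or covariate. The remaining vital-sign output is categorical ("the number and percentage of subjects who have a vital sign value meeting the criteria will be summarized") or in listings, and no between-arm estimate or interval is attached to it. SAP 10.5 then closes the list: "There will be no other safety analyses for this study".

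The SAP does specify baseline adjustment elsewhere. For continuous efficacy endpoints, SAP 9.1 uses an MMRM "adjusting for the fixed effects of treatment, actual values of stratification factors at Baseline, Baseline value, visit and treatment by visit interaction as covariates". That model sits in the efficacy section, and section 10 does not refer to it.

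Baseline blood pressure is available. Operations Manual 3.9 takes the pre-dose Day 1 reading as baseline, and Protocol Appendix D schedules vital signs at every site visit. On treatment after Week 16, SAP 2.2 says: "Starting at Week 16, all subjects will receive 150 mg of RZB every 12 weeks until the last dose at Week 40".

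**The concern.** A difference of change scores fixes the slope on baseline at 1. If baseline and follow-up readings correlate at less than 1, part of an arm's apparent change reflects where that arm happened to start. An arm that starts higher by chance will on average show a larger fall. The interval is also usually wider than one that estimates the slope from the data.

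Blood pressure has a particular place among the safety data here. Appendix D schedules chemistry and hematology at Screening, Baseline, Week 28 and Week 52, the ECG at Screening only, and weight at Screening and Week 52. Blood pressure is therefore the only continuous safety variable in the SAP's analyses with scheduled post-baseline readings under placebo control, at Weeks 4 and 16. Operations Manual 6.5 gives study drug after the other visit procedures, so the Week 16 reading still belongs to the controlled period. With about 50 subjects per arm, there is reason to use the baseline reading well.

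**Working it through.** **The plan's own figures.** The documents give no precision figure for the blood pressure comparison. Their only sample-size statement is more than 90% power for each primary endpoint with 50 per arm (SAP 2.4). It reproduces: 66% versus 13% gives 99.998% in Study-G, and 48% versus 11% gives 98.9% in Study-S. It is used below only as the source of n.

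**Inputs.**
- n = 50 per arm, 1:1 (SAP 2.4).
- SD of systolic pressure: assumed 15 mmHg, range 12 to 18, equal at baseline and follow-up. Not in the documents.
- Correlation rho between baseline and follow-up: assumed 0.5 to 0.7, with wider values checked. Not in the documents.

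**Formulas** for the between-arm difference:
- Unadjusted change: variance = 2 × SD² × (1 − rho) × 2/n.
- Adjusted for baseline: variance = SD² × (1 − rho²) × 2/n.
- Variance ratio, adjusted to unadjusted = (1 + rho)/2, so 0.75 at rho 0.5 and 0.85 at rho 0.7.
- Average shift of the unadjusted difference = (rho − 1) × baseline imbalance.
- One standard error of baseline imbalance = SD × √(2/50) = 0.2 × SD, which is 3 mmHg at SD 15.

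**At SD 15, rho 0.5.** Unadjusted SE = 15 × √(2 × 0.5 × 0.04) = 3.00; half-width 1.984 × 3.00 = 5.95 mmHg. Adjusted SE = 15 × √(0.75 × 0.04) = 2.60; half-width with multiplier 1.985 = 5.16 mmHg. Shift for a 3 mmHg imbalance = −0.5 × 3 = −1.5 mmHg.

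**At SD 15, rho 0.7.** Unadjusted SE = 15 × √(2 × 0.3 × 0.04) = 2.32; half-width 4.61 mmHg. Adjusted SE = 15 × √(0.51 × 0.04) = 2.14; half-width 4.25 mmHg. Shift = −0.3 × 3 = −0.9 mmHg.

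**Range over the assumed SD:**

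| SD (mmHg) | rho | Half-width, unadjusted | Half-width, adjusted | Size of shift at 1-SE imbalance |
|---|---|---|---|---|
| 12 | 0.5 | 4.76 | 4.13 | 1.20 |
| 12 | 0.7 | 3.69 | 3.40 | 0.72 |
| 15 | 0.5 | 5.95 | 5.16 | 1.50 |
| 15 | 0.7 | 4.61 | 4.25 | 0.90 |
| 18 | 0.5 | 7.14 | 6.19 | 1.80 |
| 18 | 0.7 | 5.53 | 5.10 | 1.08 |

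**Simulation check** (20,000 runs per rho, 50 per arm, t quantiles, one degree of freedom spent on the covariate). The mean CI width, adjusted relative to unadjusted, was 0.81 at rho 0.3, 0.87 at 0.5, 0.90 at 0.6, 0.93 at 0.7, 0.95 at 0.8, 0.98 at 0.9 and 1.00 at 0.98. The slope of the unadjusted estimate on baseline imbalance was −0.50 at rho 0.5 and −0.30 at rho 0.7; the adjusted slope was about 0. Coverage of the unadjusted CI stayed between 0.948 and 0.952.

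**The case against.** The strongest reply is that this is a choice between two valid methods for a descriptive output. That largely stands. The unadjusted difference is unbiased over randomization and its interval covers as stated. No p-value is planned for it, it lies outside the testing hierarchy in SAP 13.0, and Protocol 7.5 promises only a summary of mean changes and percentages. SAP 10.4 also displays baseline means, so a reader could see an imbalance. What remains is that the displayed interval would not account for that imbalance, although the data to do so are in hand.

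Three stronger readings are tempting, and the documents do not support them.
- **That the SAP has committed to an unadjusted analysis.** It does not say so; this is inferred from its silence, read against the explicit model in 9.1.
- **That 10.4 contradicts 9.1.** It does not. The model in 9.1 is for efficacy endpoints, and nothing extends it to safety.
- **That the SAP plans a placebo comparison in Period B.** In 10.4 the periods, the post-baseline visits and the placebo contrast appear in three separate sentences, and the last names no period or visit. SAP 4.0 assigns safety groups by the first dose received in the analysis period, so Period B has no placebo group. The wording is loose but does not prescribe an invalid comparison.

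It could also be said that changing 10.4 alone leaves SAP 10.3, which uses parallel wording for laboratory variables, on a different method. But no chemistry or hematology is scheduled at Week 4 or 16, so the scheduled placebo-controlled contrast arises for blood pressure and not for those tests.

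**Conclusion.** The point holds as a low-severity improvement. On its natural reading, SAP 10.4 leaves some precision unused and lets chance baseline imbalance move the estimate; it is not an invalid analysis. Under the assumptions above, the CI would be about 7% to 13% narrower, and the average shift avoided is 0.9 to 1.5 mmHg per 3 mmHg of baseline imbalance. These figures depend on an SD and correlation that the documents do not give. The gain is about 5% at rho 0.8 and 2% at 0.9, and it vanishes near 0.98. No efficacy conclusion or type I error statement is affected. The Period B matter is a wording clarification only.

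**What to change.** In SAP 10.4, state that at Weeks 4 and 16 the risankizumab-minus-placebo difference in systolic and in diastolic blood pressure will be estimated by ANCOVA of change from baseline on treatment and baseline value of the same measure. Report the LS mean change per arm and the adjusted difference with its 95% CI.

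As a clarification, add that the risankizumab-versus-placebo difference applies to Period A only and that Period B shows within-group changes. If the sponsor prefers to keep the unadjusted difference, one sentence saying that this is deliberate would remove the ambiguity.

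The cost is one or two sentences and a small programming change, with no new data, visits or subjects.
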